**D. Study Design/Approach.** The study will involve 22 middle schools (12 in SC, 10 in MD) in a cluster-RCT, with all schools receiving the Wellness intervention and half of the schools (6 in SC, 5 in MD) randomized to receive enhanced intervention including the two SEs (Partnership). Stratified random assignment of schools to the Wellness Group or the Partnership Group will be conducted. We will then use validated procedures (23, 24) to further stratify schools within each state. We will construct a composite inflate-suppress score derived from school data on rurality, average number of students per grade, percent white, percent receiving free/assisted lunch, and average school test performance. Rurality within the two study sites will be operationalized by using a federally developed classification system used by The US Census Bureau (i.e., a 9-point, "Rural-Urban Continuum"). The coding scheme will distinguish three metro county categories based on population size, and six non-metro county categories based on degree of urbanization, as well as adjacency to other areas and metro proximity. Per operationalization of rurality in the federally-based coding continuum, we can confirm that the SC study sites contain county classifications of rural and suburban, while the MD site is exclusively urban. We will separate this composite into three strata and randomly assign schools from these strata to receive either the Wellness Group or the Partnership Group.

In the 5-year longitudinal design, Year 1 will involve administrative start up, collection of pre-assessments and intervention launch; Years 1-4 will involve intervention versus comparison while participants are in 6th through 8th grades. Year 5 will involve analyses and dissemination. A comprehensive implementation manual will guide the study and will be updated and improved regularly through active guidance of a Stakeholder Advisory Board (SAB, see Tables 3 and 4 in Appendix). The SAB will provide significant input as this manual is developed during the study start-up period from January through July, 2019, and progressively improved through study duration (see Gantt chart in Figure 1 of the Appendix for a review of all study activities in time).

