**Analytic Plan.** The proposed project is a cluster-randomized controlled trial (J=22 schools; 11 per treatment arm) comparing the efficacy of Wellness vs. Partnership services. As a general analytic plan, we will use hierarchical linear modeling (HLM) to evaluate the project aims. Specifically, we will use two-level HLM models to account for students being nested within schools. Though one might conceptualize this proposal as a three-level model (i.e., students nested within schools, and schools nested within sites), it would be neither feasible nor recommended to model site as a multilevel variable given there are only two sites in the design (56). In line with best practice, we will integrate site (i.e., SC vs. MD) as a covariate in the statistical models to contain any potential effects of this variable. Based on prior research conducted by the team, we expect intraclass correlations (ICCs) to warrant the incorporation of random intercepts to account for violations of independence. We will also test independence assumptions for the treatment parameters to determine how sensitive treatment effects are to potential violations of independence, and will include random slopes to account for nested treatment effects if ICCs exceed .01. For transparency, we will report both fixed and random effects (i.e. intercepts and slopes) of the model. Additionally, we will iteratively subset the model using a k-1 sensitivity analysis to determine the influence of individual sites on parameter estimates. We will estimate statistical models using full information maximum likelihood to accommodate any missing data (57). We will use maximum likelihood with robust standard errors to estimate models that include the Zero Inflated Poisson link function for count

PRINCIPAL INVESTIGATOR: [name]

outcomes (e.g. absences, referrals). This general analytic framework will be used in aims 1 and 2. Details, exceptions, and modifications to it are discussed below.

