*Model modifications for students receiving tier 3 services.* To evaluate the effects of the enhanced treatment on students who receive tier 3 clinical services, and to accommodate the fact that there will be a rolling admission into clinical services, the treatment parameter will be interacted with a dosage parameter measuring each individual student's weeks of treatment received. This interaction term will provide a treatment effect estimate that is calibrated by dosage, as measured by weeks of treatment received. Because we will use an active treatment, we will be able to detect treatment-by-dosage differences between the enhanced and control treatments. To accommodate the possibility that random assignment does not create exactly equal groups with K=22, and to provide interpretable estimates of change in response to the intervention, we will use difference scores as the dependent variable unit of analysis for students receiving tier 3 clinical services. This will facilitate the direct examination of how services received over time influences youth change. The null hypothesis associated with change scores is that baseline differences remain constant and there would thus be no mean change across measurement occasions. Rogosa and colleagues (58-60) highlight the utility of using difference scores to evaluate pretest-posttest change in similar studies, indicating that previous work critical of this approach has been misleading in that it focused on several restrictive assumptions including high correlations of pretest and posttest measures as well as equal variances across measures over time. Given our previous research, outcomes, and statistical model, we believe that difference scores are the appropriate dependent variable.

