Given the experiment will examine intent-to-treat effects in a real-world setting, we will conduct analyses to investigate variability in implementation and compliance to enhance causal effect interpretation of clients "as treated." Specifically, we will use a Bayesian Additive Regression Tree approach (BART; 61) to delineate the impact of key treatment assumptions (e.g., compliance, fidelity, etc.), as well as to estimate the impact of assumption violations on the estimation of causal effects in the design. BART is an extension of Classification and Regression Tree (CART) models that is based on a recursive partitioning algorithm that explains variation in the outcome through repeated splits of the data into homogenous subgroups that are similar on predictor variables. One significant strength of BART is that it is capable of handling a large number of predictors and incorporates higher-order interactions that may be excluded from parametric analysis. Research indicates that BART is insensitive to tuning parameters and produces more accurate estimates of treatment effects compared to other methods of analyzing treatment effect heterogeneity (i.e., propensity score matching, propensity-weighted estimators, instrumental variable procedures, and regression adjustment; 61). Note that this BART enhancement to the randomized, experimental design should not be mistaken for a Bayesian trial design.

*Power considerations.* The design originally included a planned sample size of approximately N=2800 (1400 per arm) for Aims 1 and 2. We previously revised power estimates for these study aims that consider the possibility of reduced participant involvement given COVID-19 and recruitment challenges more broadly, with a revised sample size of approximately N=1400 (700 per arm). With the research study period concluding in June 2023, we have revised the enrollment projection to a conservative estimate of N=1225. With our currently active sites (J=22) and the total number of students enrolled in the study (N=1225, including expected spring 2023 enrollment), assuming 30% of variance

PRINCIPAL INVESTIGATOR: [name]

explained in the primary outcomes by pre-test covariates, and 80% power, we have a minimum detectable effect size (MDES) of .29. If we reach our goal of 1400 students, we will be at .28.

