*Study retention.* Due to documented accessibility advantages of SBH (16) and our past experiences, Tier 3 students and parents are likely to remain involved in the study throughout the span of treatment. Additionally, the intervention requires no extra effort to participate outside of the assessments, with similar types of assessments routinely used in treatment for progress monitoring. In similar studies conducted, the most common reason for study attrition was due to students transferring to another school, which has been nominal across school wide populations. However, Tier 3 students experiencing EB problems are more likely to transfer schools than the general population.

*Incorporating research activities into routine care.* All research activities will be included in routine SBH functions. Consent to participate will be integrated into the existing process that clinicians use to obtain consent for treatment. Students and their parents may notice that their clinician is utilizing some new strategies, however all within parameters of expected clinical care. The same is true in the Partnership condition, will all enhancements those that would logically occur in a school embracing innovation and pursuing holistic strategies to remove barriers to student learning.

*Training and experience of recruitment personnel.* For students receiving Tier 3 services, the 20 clinicians will assist in study recruitment. Beginning in Year 2, a clinician was added in two [REDACTED] schools, one per condition for a total of 22 clinicians. Beginning in Year 3, two additional schools were added, one per condition, for a total of 22 schools and 24 clinicians. All clinicians will have a master's degree in a behavioral health discipline (e.g., psychology, counseling, social work) and will hold a valid license to provide psychological services or be under the supervision of a licensed clinician. Each clinician will participate in human subjects training prior to recruitment efforts and will be trained by the research team on recruitment procedures. The Lead Research Manager, [name], will oversee recruitment efforts with the PI, [name] and Co-I/MD Site PI, [name], as guided by the SAB and building on experiences from prior RCTs conducted

PRINCIPAL INVESTIGATOR: [name]

by the research team, including a large current RCT funded by the National Institute of Justice that includes an opt-out procedure. See below for recruitment parameters.

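### The planned random slope on treatment has no usable variance because each school has one arm, and uncorrected maximum likelihood on 22 schools gives about 6.7% to 8.4% false positives at an assumed 5% level

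*Combined protocol and SAP*

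**What the plan says.** Section D (Study Design/Approach) forms strata of schools and will "randomly assign schools from these strata to receive either the Wellness Group or the Partnership Group". The Analytic Plan describes 22 schools, 11 per arm, analysed with two-level models of students within schools, a school random intercept, and site (SC or MD) as a covariate.

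For the treatment parameters, the plan "will include random slopes to account for nested treatment effects if ICCs exceed .01". It adds that "we will report both fixed and random effects (i.e. intercepts and slopes) of the model". No covariance structure is given for the random effects.

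On estimation it says "We will estimate statistical models using full information maximum likelihood to accommodate any missing data". For counts it says "We will use maximum likelihood with robust standard errors to estimate models that include the Zero Inflated Poisson link function for count" outcomes, with absences and referrals as examples. The framework applies to Aims 1 and 2. No section states alpha, an ICC, a degrees-of-freedom rule, a reference distribution or a small-sample correction.

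For Tier 3 students, the subsection on model modifications says "the treatment parameter will be interacted with a dosage parameter", namely each student's weeks of treatment.

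**The concern.** There are two separate problems.

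First, a random slope on treatment describes how the treatment effect varies from school to school. To see that variation, some schools would need students in both arms, and here none has them. The plan nevertheless commits to fitting and reporting this quantity.

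Second, the information about a school-level treatment effect comes from 22 schools, however many students are enrolled. Full maximum likelihood makes no allowance for the fixed effects when it estimates the between-school variance, so it underestimates that variance when clusters are few. Uncorrected cluster-robust errors are also too small. Intervals are then too narrow, and the chance of declaring a Partnership benefit that does not exist exceeds its nominal value. The power statement rests on the intent-to-treat effect, which is a school-level contrast. The trial is meant to tell school and mental health systems whether to invest in these enhancements, so the error rate matters.

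**Working it through.** **Inputs.** From the Analytic Plan: J = 22 schools, 11 per arm, site as covariate. Intercept, arm and site make p = 3 school-level terms, leaving 22 − 3 = 19 degrees of freedom. From Power considerations: N = 1,225, about 55.7 students per school. Two-sided 5% alpha and the ICC are assumptions, because the plan states neither. The Comparators subsection gives a different split of schools by site and arm and should be reconciled with Section D. The total of 22, and hence the 19 degrees of freedom, is unaffected.

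**The plan's own figure.** Its only design figure is a minimum detectable effect of .29 at 80% power, with 30% of variance "explained in the primary outcomes by pre-test covariates". Without an ICC or alpha it cannot be reproduced directly. Back-solving from

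MDES = (t.975 + t.80) × √[ICC(1−R²₂)/(J/4) + (1−ICC)(1−R²₁)/(N/4)]

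with 20 degrees of freedom, where R²₁ and R²₂ are the student- and school-level shares explained, gives an ICC of .059 if the 30% applies at both levels, .052 if at school level only, and .041 if at student level only. The implied ICC is above the .01 trigger, but whether each outcome meets the trigger is unknown.

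**Identification.** Let t00 be the intercept variance, t11 the slope variance and t01 their covariance. Between-school variance is t00 in Wellness schools and t00 + 2·t01 + t11 in Partnership schools. The map from three parameters to these two quantities has rank 2. For example, (t00, t01, t11) = (.05, 0, .03), (.05, −.02, .07) and (.05, .01, .01) all give school variances of .05 and .08. The data cannot distinguish slope variances of .03, .07 and .01.

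**Type I error by formula.** With equal school sizes and a variance estimate above zero, ML divides the school-level residual sum of squares by 22 instead of 19. The SE ratio is √(19/22) = .929, which is 7.1% too small. Then:

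- ML with z: P(|t19| > 1.960 × .929) = 8.43%, so a nominal 95% interval covers about 91.6%.
- ML with t19: P(|t19| > 2.093 × .929) = 6.67%, coverage about 93.3%.
- REML with z: P(|t19| > 1.960) = 6.48%.
- REML with t19: 5.0%.

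**Simulation under the null.** Linear models: 12 SC and 10 MD schools, 11 per arm, about 56 students per school, ICC .02, .05 or .10, coefficient of variation (CV) of school size 0 or .5, 4,000 runs per setting (Monte Carlo SE about 0.45 points). Zero-inflated Poisson: marginal model with arm and site, assumed 40% structural zeros, mean count 3, school SD of log count .15, .30 or .50, school-size CV 0 or .5, 1,500 runs per setting (Monte Carlo SE about 0.7 points).

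| Analysis | z reference | t19 reference |
|---|---|---|
| ML, random intercept | 8.4–9.1% | 6.2–7.2% |
| ML, arm-specific school variances | 8.3–9.1% | 6.1–7.0% |
| REML | 6.1–7.0% | 4.5–5.3% |
| Zero-inflated Poisson, uncorrected school-clustered sandwich | 8.4–11.5% | 6.7–10.0% |

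The second row is the identified part of the slope model, and it shows that the slope rule barely moves the test. A wider set of linear runs (ICC .01 to .20, equal and unequal school sizes, 6,000 runs each) gave ML 7.3–9.4% with z and 5.8–7.7% with t19. Further zero-inflated Poisson runs with 56 and 300 students per school gave 8.2–9.7% and 6.0–8.3%.

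**Sensitivity of the ML formula (z, t).** No site term: 7.6%, 6.1%. Two more school-level terms: 10.3%, 8.1%. Twenty schools with p = 3: 8.9%, 6.9%.

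**The case against.** The plan gives no covariance structure. If the intercept-slope covariance is fixed at zero, the slope variance can be estimated. That is correct, but the plan states no such constraint. The number obtained would then be only the excess between-school variance in Partnership schools, not the spread of treatment effects. A slope on weeks of treatment does vary within school and can be estimated, so the criticism is confined to the treatment indicator. The slope rule has little effect on the treatment test. Convergence failure is possible but was not demonstrated.

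On inference, the plan is silent about corrections and does not say there will be none, and no section specifies a normal reference. The 8.4% figure does need a normal reference. With t19 the excess is about 1.7 points. The point does not rest on silence alone, however, because the stated estimator is anti-conservative under either reference. The inflation also varies: near ICC .01 with equal school sizes it is about 7.3% (z) and 5.8% (t19), because the variance estimate often falls to zero.

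The count figures are the softest. They come from a marginal model with assumed count parameters, whereas the plan's general framework has school random intercepts. The 300-student runs show that the inflation is not an artefact of small schools, but these rates are best read as illustrative.

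Full maximum likelihood was chosen to handle missing data. That purpose is legitimate, and any replacement has to preserve it.

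**Conclusion.** The concern holds on both parts and should be fixed. With a free covariance the treatment-slope variance is not identified; with the covariance fixed at zero it is not a treatment-effect variance. Either way the promised report would mislead, although the treatment estimate and its test are little affected.

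For school-level treatment contrasts, uncorrected ML has a false-positive rate of about 6.7% (t19) to 8.4% (z) instead of 5%. This assumes a two-sided 5% level, three school-level fixed effects and roughly equal school sizes. The direction is the same across the ICCs, school sizes and numbers of school-level terms examined. The figures do not cover the Tier 3 treatment-by-weeks interaction, which varies within school.

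**What to change.** - Delete the random-slope rule for treatment, or relabel it as arm-specific between-school variance. Keep the planned school random intercept.
- State alpha, sidedness and the reference distribution.
- Fit continuous outcomes by REML with Kenward-Roger or between-school t degrees of freedom. REML with a normal reference is not enough, at about 6.5%.
- Add multiple imputation if pre-test covariates are missing, because REML alone handles only missing outcomes, under missing at random.
- For count models, use a small-sample-corrected school-level sandwich with a t reference.
- A permutation test is an alternative only if it follows the actual allocation. The subsection on recruitment personnel says "Beginning in Year 3, two additional schools were added, one per condition", and the plan should state how those two were assigned.

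**Cost.** Intervals for school-level contrasts widen by 1/.929 = 1.076, about 8%, relative to ML with t19, and by 2.093/(1.960 × .929) = 1.149, about 15%, relative to ML with z. Imputation and documenting the Year 3 allocation add some analysis work. No new data are needed.

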complete the survey, which assesses the dimensions of engagement, safety, and environment once annually at the end of each academic year for the four years of intervention vs. comparison (2019-20, 2020-21, 2021-22, 2022-23). Due to the COVID-19 pandemic, the team was unable to collect SCS data from students in [REDACTED] schools during the first academic year (2019-2020). While this means a compromised set of Year 1 data on school climate for the [REDACTED] site, such measurement is intact for SC, and we will still be able to document trends in time in school climate in [REDACTED] for years 2-4 of the intervention vs. comparison period. Additionally, the study team will collect rosters of classrooms receiving The Guide Curriculum (GC). This will enable two sets of analyses: first, we will document which students receiving Tier 3 services and participating fully in the study are exposed to GC and account for this in terms of interventions received in analyses. Second, this will significantly expand a second level of enrollment for the study, as we will have de-identified academic records for all students (related to recently approved amendments), and will explore impacts of the GC on academic record variables (e.g., discipline problems, grades, attendance) for students in classrooms in Partnership schools receiving it compared to students in demographically comparable classrooms from Wellness schools that do not receive it.

The second stream of data collection will focus on students receiving Tier 3 services and consenting to be in the study. Clinicians will collect these measures with students and families at intake, every three months, and at case closure, using an electronic data portal coordinated by [name] and the Informatics Team at the Medical University of South Carolina (MUSC). The measurement strategy for each of the study aims is presented here:

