*Aim 2: Evaluate the impact of the Partnership enhancements on students' social, emotional/behavioral (EB), and academic outcomes.* For this primary aim, there will be two sub-aims: Aim 2a will evaluate the impact of the Partnership enhancements on school-wide academic record variables of grades, attendance, lateness and discipline referrals. Aim 2b will focus on students receiving Tier 3 services and will assess their social and emotional/behavioral (EB) functioning. To assess social functioning, the Child and Adolescent Social and Adaptive Functioning Scale (51) will be completed by students. The CASAFS includes 24 items measuring students' functioning in four key social roles: school performance, peer relations, family relations, and home duties/self-care. Additionally, both "internalizing" EB problems, which include problems of depression, anxiety and exposure to trauma, and "externalizing" EB problems, which include conduct and attention problems, will be measured for students receiving Tier 3 services. Student EB functioning will be measured by parent and student report forms of the Brief Problem Checklist (52), a 12-item questionnaire that measures externalizing and internalizing problems. Derived from the comprehensive Child Behavior Checklist (53), it is designed for repeated periodic assessment of clinical progress, yielding both an internalizing and externalizing subscale (52). Please note that academic variables collected above school-wide for stream 1 data collection, will also be used for stream 2 data collection for students receiving Tier 3 services. Changes in the above variables will be assessed for students for the academic quarter before receiving mental health services and the academic quarter after services have been completed.

*Additional Measures.* In addition to measures directly reflecting study aims, secondary aims will be addressed by measures reflecting the potential impact of the two Partnership enhancements will be collected at the same time intervals for students receiving Tier 3 services. For the enhancement focused on mental health education and stigma reduction, students will complete The Guide Curriculum Assessment (GCA) reviewed previously (43,44). The GCA includes subscales assessing Mental Health Literacy in three dimensions: Mental Health Knowledge (MHK; 28 items),

PRINCIPAL INVESTIGATOR: [name]

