Estimating dose-response effects using a conventional, frequentist treatment\*dosage interaction would violate the strong ignorability assumption, confound effects with varying characteristics of participants and sites, and yield biased estimates (e.g., 69,70). The BART models proposed in the current application have demonstrated efficacy in estimating treatment effects in quasi-experimental studies that may vary as a function of a continuous variable, such as treatment dose (71). The BART approach will provide an estimate of the treatment effect for those who received the intervention conditional on baseline covariates (i.e., conditional treatment effect on treated). We will calculate conditional treatment effects on treatment for each individual following the Neyman-Rubin causal model (72,73). The BART models will yield an effect size for each varying level of exposure, as well as provide a credible interval (analogous to a frequentist confidence interval) for the effect estimate. The BART models will also allow missing data to be included as a feature in the predictive model using a "missingness incorporated in attributes" approach. This means that BART will use all available data. Kapleiner and Bleich (74) demonstrated that this approach is computationally efficient and that results are comparable to other advanced missing data approaches (e.g., multiple imputation).

We will conduct additional analyses to ensure the results from our original models are not due to random noise in the sample. Specifically, we will conduct 250 Monte Carlo simulations in which a random binomial variable will be generated to represent an instrumental variable such that it will be uncorrelated with covariates or outcomes. Then we will regress each of the outcomes on the binomial variable yielding a parameter representing the relationship between the instrumental and binomial variable that is unrelated to the outcomes. This analysis will test the sensitivity of our BART models on estimated treatment effects and determine how robust our credible intervals are.

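### For the Tier 3 change outcomes, full information maximum likelihood on a single difference score is a complete-case analysis, so the claim to accommodate any missing data does not hold there

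*Combined protocol and SAP*

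**What the plan says.** The Analytic Plan sets the general model: "we will use two-level HLM models to account for students being nested within schools". Its missing-data provision is one sentence: "We will estimate statistical models using full information maximum likelihood to accommodate any missing data (57" (57 is a reference number).

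The subsection on model modifications for Tier 3 students then fixes the outcome: "we will use difference scores as the dependent variable unit of analysis for students receiving tier 3 clinical services". It does not say which follow-up assessment is subtracted from intake.

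Under Measures and Measurement Plan, the Tier 3 scales are measured repeatedly: "Clinicians will collect these measures with students and families at intake, every three months, and at case closure".

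For the BART analyses, the text under Power considerations says the models will "allow missing data to be included as a feature in the predictive model", through missingness incorporated in attributes, and concludes: "This means that BART will use all available data".

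No attrition rate is given. Study retention expects Tier 3 families to stay through treatment, but adds that "Tier 3 students experiencing EB problems are more likely to transfer schools than the general population". I found no stated missingness assumption, no auxiliary variables and no sensitivity analysis for data missing not at random.

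**The concern.** Full information maximum likelihood recovers information about a missing score only through other observed outcomes in the same model. Here the model has two levels, students and schools, and one outcome value per student. There is no level for scores within a student through which an intake or 3-month score could inform a missing later one.

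The statement that missing data are accommodated is therefore untrue for CASAFS and the Brief Problem Checklist. These belong to Aim 2, which the plan calls primary. Partnership is meant to change engagement, alliance and dose (Conceptual Framework), so loss that differs by arm is a possibility the analysis should be able to absorb. If loss depends on scores already observed, the planned contrast can be biased although the data to correct it are in hand.

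**Working it through.** **1. The likelihood.** For school j, let O_j be the students with an observed difference score d. The school contributes the normal density of {d_ij : i in O_j}, with covariance σ²I + τ²11′. A missing d_ij integrates to 1. In a simulated set of 1225 students, 862 had a score. The log-likelihood was -1218.7406 over all 1225 and -1218.7406 over the 862 alone. The method is the same as complete-case analysis.

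**2. The stated detectable effect, and the precision cost.** Power considerations gives .29 at N=1225 and .28 at N=1400, with 22 schools, 30% of variance explained and 80% power. The ICC and alpha are not stated. I assume ICC .04, two-sided alpha .05, the 30% at student level only, and 20 df:

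- MDES = M·√[ICC/(.25·22) + (1−ICC)(1−.30)/(.25·N)], with M = t(.975) + t(.80) = 2.946.
- N=1225: 2.946·√(.007273 + .002194) = .287.
- N=1400: 2.946·√(.007273 + .001920) = .282.

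These round to the stated figures, but other assumptions also fit, so this is not a confirmation. With the ICC set to give exactly .29 (.0412), losing 10, 30 or 50% of follow-up scores (1102, 858 or 612 students left) gives about .294, .304 and .321. The school term dominates, so the precision loss is small.

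**3. Bias.** All of the following are assumptions: no true arm effect; intake, 3-month and 6-month scores with unit SD and correlations .70, .70 and .55 (intake with 6 months); higher score worse; no clustering; odds ratio for loss 1.6 to 2.2 per SD of the driver; 2,000,000 students per arm. Entries are Partnership minus Wellness, in SD. Joint use predicts the missing 6-month score from the intake and 3-month scores within arm.

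| Loss depends on | Missing, Wellness/Partnership | Fixed 6-month difference | Last available follow-up | Joint use |
|---|---|---|---|---|
| 3-month change, Wellness only | 30/30% | +.08 to +.12 | −.02 to −.03 | 0.00 |
| 3-month level, Wellness only | 30/30% | 0.00 | −.03 to −.04 | 0.00 |
| Intake score, Wellness only | 30/30% | −.06 to −.09 | −.01 to −.02 | 0.00 |
| 3-month change, both arms alike | 37/19% | +.05 to +.07 | −.01 | 0.00 |
| 3-month change, both arms alike | 30/30% | 0.00 | 0.00 | 0.00 |

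In the 37/19% row, the last-available figure becomes −.04 to −.05 if both arms improve by .2 SD every three months.

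Adding intake as a covariate removes the bias in the intake row. It leaves about .05 to .09 in the first row, and creates about .04 to .07 in the second.

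A separate run with correlations .5 to .7 and a steeper dependence (log-odds 1 per SD) on intake gave .13 for the difference score when one arm was affected, and .26 when the arms were affected in opposite directions. Joint use again gave 0.00. When loss depended on the unseen outcome differently by arm, joint use was also biased (−.14 to +.27), so a sensitivity analysis is needed as well.

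**4. BART.** Attributes are predictors. The described method splits on missing predictors, and no step is given for a student with no outcome.

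**The case against.** The strongest reply is that the plan never fixes a 6-month endpoint. A student whose case closes early has a closure score, and one with only a 3-month score could be kept. This stands: if the last available follow-up is used, the .08 to .12 falls to .02 to .03 with the opposite sign. Students certain to be lost are those with no follow-up at all, and they have no interim score to recover.

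It also stands that the simulated contrasts leave out the weeks-of-treatment term and its interaction with arm, which the Tier 3 model contains. The figures are therefore not the bias of the planned estimator. Power considerations mentions pre-test covariates, so intake may be intended as a covariate, although the Tier 3 text does not list it. Step 3 shows that this would cure only loss driven by intake.

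Three stronger readings are tempting but not supported:

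- **That the plan itself shows non-responders leaving.** Study retention compares Tier 3 students with the general population on school transfer. It says nothing about who leaves within Tier 3, or about arms.
- **That missing data are mishandled throughout the trial.** Aim 1 session counts and Aim 2a school-wide records are not difference-score outcomes.
- **That the BART text makes a false claim about outcomes.** It is written in predictor language and serves a supplementary analysis. It needs a clarifying sentence.

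Difference scores are a deliberate and argued choice, and nothing here forbids them as an estimand. The objection does not touch step 1: whichever follow-up is chosen, a student without it contributes nothing.

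**Conclusion.** The point holds for CASAFS and the Brief Problem Checklist in Tier 3 students. The stated property of the missing-data method fails there, and intake and interim scores that are already collected go unused for students without the follow-up score.

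The bias cannot be fixed from the documents. Under the main assumed settings with arm-differential loss it is about 0 to .12 SD for a fixed 6-month difference (at most .12/.29 = 41% of the stated MDES), and about .02 to .04 SD for the last available follow-up (.01 to .05 across every unequal-loss setting tried). A reader might infer that the Tier 3 result will be off by a large share of the detectable effect. The documents do not support that, because equal loss with equal dependence gave no bias and the mechanism is unknown. What favours a change is that joint use of the scores was unbiased in every setting where loss depended on observed scores. Severity: should-fix.

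**What to change.** In the Analytic Plan and its Tier 3 subsection:

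- Fit CASAFS and the Brief Problem Checklist with a likelihood-based repeated-measures model: scores within students within schools, arm by time, and the site covariate.
- Include intake and every observed follow-up at its actual time since intake. Closure scores enter at their own time, not as a common visit, because closure time varies and service duration is itself a hypothesised outcome.
- Take the arm contrast in change at a time point named in advance. The difference score may stay as a supporting analysis, with its follow-up defined.
- State the missing-at-random assumption, report missingness by arm, and add one delta-adjusted sensitivity analysis that shifts the missing scores by arm.

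In the BART text, say that missingness incorporated in attributes covers missing predictors only, and that students without an outcome are either excluded or given multiply imputed outcomes.

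The cost is a somewhat more complex model and revised wording. No new data are needed.
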